4.2 Methods for Handling Dose Changes

All subjects are scheduled to receive 6 weekly doses of RGI-2001 100 µg/kg via IV administration. Deviations from this schedule or dose will be included in the administration list, and will also be displayed in the summary table that is analyzed with continuous methods (e.g., displaying mean, minimum, and maximum).

4.3 Methods for Handling Missing Data

No imputations will be made for missing data, except as described for the time-to-event analyses in Section 4.1 (above).

4.4 Interim Analysis

There will be no interim analyses described within the scope of this SAP.

5.0 STUDY SUMMARY

5.1 Subject Disposition

Subject disposition will be summarized for all subjects by frequency counts and percentages of completed and discontinued status along with reason for discontinuation. This summary analysis will be based on all subjects in the clinical study database. Subject disposition for all subjects will be listed. Furthermore, a summary table for death will be reported.

5.2 Protocol Deviations

A by-subject listing will be provided for all protocol deviations for all subjects. Major Protocol deviations will be summarized in a table.

6.0 EVALUATION OF DEMOGRAPHICS, BASELINE CHARACTERISTICS, AND PROPHYLACTIC TREATMENT

All analyses in this section will be performed using the Safety Population.

6.1 Demographics

Using the Safety Analysis Population, demographics (age, sex, race, and ethnicity) will be summarized using categorical and continuous methods, as appropriate. A by-subject listing will also be provided.

6.2 Baseline Characteristics

A by-subject listing will be provided with height, weight, and BMI. In addition, a summary table will be provided.

6.3 Disease Status Prior to HSCT

A table will be provided to summarize: time since initial diagnosis, type of disease prior to HSCT, and other pre-enrollment disease characteristics collected on the *Initial Disease Status and Evaluation Prior to HSCT* eCRF. A by-subject listing will also be provided.

6.4 Graft Source and Donor Characteristics

A table will be provided to summarize: donor/recipient sex matching, graft source, donor relationship to the subject, and donor/recipient CMV serostatus. A by-subject listing will also be provided.

6.5 Preparative Conditioning Regimen

A summary table will be provided. In addition, a by-subject listing will be provided with regimen, dose, route, start date, and other preparative information.

6.6 Concomitant Medications

Per protocol, concomitant medications are any prescription or over-the-counter preparations used from 2 days prior to the preparatory regimen before Day 0 through the end of the subject’s study participation.

Medications will be coded using the World Health Organization (WHO) Drug Reference List version 1Q2019. These will be summarized via categorical methods by ATC class and preferred term, and all will be provided in a by-subject listing.

In addition to the summary table for all concomitant medication, two subset tables will be presented. The first will be a summary table to describe the concomitant medications given as aGvHD prophylaxis. The second will be a summary table to describe the concomitant therapies given as treatment for GvHD with the first 100 days. This second table will include a summary of the total dose received. Total Dose will be calculated as: Daily Dose (in mg units) * Adjusted_Duration (in days), where Daily Dose and Adjusted_Duration are defined per below using the start/stop/frequency/unit information recorded on the Concomitant Medication eCRF.

Daily Dose	First calculate, Dose_mg: 
 • If “Dose Unit” (on eCRF) = mg then Dose_mg = “Dose” (from eCRF) • If the “Dose Unit” (on eCRF) not mg then calculate the dose for conversion to mg Next calculate, Daily_Dose: 
 • If “Frequency” (on eCRF) = daily then Daily_Dose = Dose_mg • If “Frequency” (on eCRF) = twice daily then Daily_Dose = Dose_mg*2 • If “Frequency” (on eCRF) = every other day then Daily_Dose = Dose_mg*0.5 • If “Frequency” (on eCRF) is specified differently than the examples above, use similar logic to adjust in order to obtain the “Daily Dose”.
Adjusted_Duration (days)	First a Day100 variable: 
 • Day100 = Date of first treatment with RGI-2001 (ie, Start Date [Day 0]) plus 100 Next calculate, Adjusted_Duration: 
 • If Stop Date is provided and Stop Date ≤ Day100 then Duration = Stop Date minus Start Date plus 1. • If Stop Date is provided and Stop Date > Day100 then Duration = Date_100 minus Start Date plus 1. • If Stop Date is not provided then Duration = Day100 minus Start Date plus 1.

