11.2 Summary Tables to Be Provided

Table 11.2 Summary Tables

Table Number and Title	Analysis Population
Table 14.1.1: Subject Disposition (All Subjects)	All
Table 14.1.2: Deaths	Safety Analysis
Table 14.1.3: Subject Enrollment by Site	Safety Analysis
Table 14.1.4: Major Protocol Deviations	Safety Analysis
Table 14.1.5: Demographics	Safety Analysis
Table 14.1.6: Study Disease Characteristics	Safety Analysis
Table 14.1.7: Donor Characteristics (Safety Population)	Safety Analysis
Table 14.1.8: Conditioning Regimen (Safety Population)	Safety Analysis
Table 14.1.9: RGI-2001 Treatment Exposure (Safety Population)	Safety Analysis
Table 14.1.10: Concomitant Medications (Safety Population)	Safety Analysis
Table 14.1.11: Concomitant Medications Given as Acute GvHD Prophylaxis (Safety Population)	Safety Analysis
Table 14.1.12: Systemic Steroids and Other Therapies Given for Treatment of GvHD (Safety Population)	Safety Analysis
Table 14.2.2.1: Acute GVHD Incidence (Safety Population)	Safety Analysis
Table 14.2.2.2: Chronic GVHD Incidence (Safety Population)	Safety Analysis
Table 14.2.2.3: Acute GVHD by Organ by Stage by Keystone Criteria - Incidence (Safety Population)	Safety Analysis
Table 14.2.2.4: Acute GVHD by Organ by Stage by MAGIC Criteria - Incidence (Safety Population)	Safety Analysis
Table 14.2.2.5: Acute GvHD-Free Survival (GFS) using Keystone Criteria (Safety Analysis Population)	Safety Analysis
Table 14.2.2.6: Non-Relapse Mortality (NRM) (Safety Analysis Population)	Safety Analysis
Table 14.2.2.7: GvHD-Free, Relapse-Free survival (GRFS) (Safety Analysis Population)	Safety Analysis
Table 14.2.2.8: Overall Survival (OS) (Safety Analysis Population)	Safety Analysis
Table 14.2.2.9: Relapse-Free survival (RFS) (Safety Analysis Population)	Safety Analysis
Table 14.2.2.10: Time to Myeloid Engraftment (Safety Analysis Population)	Safety Analysis
Table 14.2.2.11: Time to Platelet Engraftment Criteria (Safety Analysis Population)	Safety Analysis
Table 14.2.3: Karnofsky Performance Status – Observed and Change from Baseline (Safety Population)	Safety Analysis
Table 14.3.1.1: Summary of Treatment-Emergent Adverse Events (Safety Population)	Safety Analysis
Table 14.3.1.2: Treatment-Emergent Adverse Events - Incidence by SOC and Preferred Term (Safety Population)	Safety Analysis
Table 14.3.1.3: Serious TEAEs – Incidence by SOC and Preferred Term (Safety Population)	Safety Analysis

Statistical Analysis Plan

REGiMMUNE Corporation

Protocol: RGI-2001-003

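### With a blank stop date, SAP 6.6 runs a GvHD drug on to Day 100 even after death, which overstates total dose in descriptive Table 14.1.12

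*SAP*

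**What the plan says.** SAP Section 6.6 plans a table of therapies given to treat GvHD in the first 100 days: "This second table will include a summary of the total dose received". By its title this is "Table 14.1.12: Systemic Steroids and Other Therapies Given for Treatment of GvHD (Safety Population") in SAP Section 11.2.

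The quantity is defined as "Total Dose will be calculated as: Daily Dose (in mg units) * Adjusted_Duration (in days"), and its components are derived "using the start/stop/frequency/unit information recorded on the Concomitant Medication eCRF". The time limit is a fixed date for each subject: "Day100 = Date of first treatment with RGI-2001 (ie, Start Date [Day 0]) plus 100".

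Duration then has three branches:

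- Stop date present and not after Day 100: "If Stop Date is provided and Stop Date ≤ Day100 then Duration = Stop Date minus Start Date plus 1".
- Stop date present and after Day 100: counted from the start date to Day 100, inclusive.
- Stop date blank: "If Stop Date is not provided then Duration = Day100 minus Start Date plus 1".

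On missing data generally, SAP Section 4.3 states: "No imputations will be made for missing data, except as described for the time-to-event analyses in Section 4.1 (above").

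**The concern.** The blank-stop branch treats every such record as therapy continuing to Day 100. That is correct for a subject who is followed to Day 100 and still on the drug. It is wrong for a subject who died earlier: the table would report as received doses that could not have been given.

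The rule also sits badly with the rest of the SAP:

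- Section 6.6 limits concomitant medications to those used up to the end of study participation, so days after death fall outside its own definition.
- Section 4.3 allows no imputation outside the time-to-event analyses, yet filling a blank stop date with Day 100 is an imputation and is not listed there.
- Section 4.1 flags assumed dates in the listings for time-to-event data. Section 6.6 asks for no flag.
- Section 9.1 makes an exception in the duration of an adverse event that is ongoing at exit. Section 6.6 has no exit provision.

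At stake is the accuracy of one descriptive summary. For deaths the error runs in one direction and falls only on subjects who died while on GvHD treatment, so it raises the mean and the maximum.

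**Working it through.** The documents give no total-dose figure, so there is nothing to reproduce. The check applies the SAP rule as written and compares it with the same rule ended at death.

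**Inputs.** The duration rule and the Day 100 definition come from SAP 6.6. The 50 treated subjects come from SAP 2.3. The Day-100 non-relapse mortality (NRM) rates come from Protocol 12.4: 10% is the level called excessive, and 5% and 20% are the Table 4 scenarios. Start days, death days and doses are my assumptions.

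**Formulas.** Let S be the start day and D the day of death, with first infusion as Day 0.

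- SAP rule, blank stop date: 100 − S + 1
- Ended at death: D − S + 1
- Excess days: (100 − S + 1) − (D − S + 1) = 100 − D
- Ratio: (101 − S) / (D − S + 1)

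| S | D | SAP rule (days) | Ended at death (days) | Excess (days) | Ratio |
|---|---|---|---|---|---|
| 30 | 45 | 71 | 16 | 55 | 4.4 |
| 30 | 50 | 71 | 21 | 50 | 3.4 |
| 20 | 95 | 81 | 76 | 5 | 1.07 |
| 40 | 45 | 61 | 6 | 55 | 10.2 |
| 60 | 70 | 41 | 11 | 30 | 3.7 |

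For starts on Days 20 to 60 and deaths on Days 45 to 95, the excess is 100 − 95 = 5 to 100 − 45 = 55 days. The ratio is larger still when death falls on or just after the start day: S = D = 60 gives 41 days against 1.

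**In milligrams.** At an assumed 140 mg/day, start Day 30 and death Day 45 give 71 × 140 = 9,940 mg against 16 × 140 = 2,240 mg. The dose cancels in the ratio, which stays at 4.4.

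**Are early deaths to be expected?** With 50 subjects, NRM of 5%, 10% and 20% gives 2.5, 5 and 10 expected non-relapse deaths by Day 100. The chance of at least one is 1 − 0.95^50 = 92%, 1 − 0.90^50 = 99.5%, and over 99.9%. These are chances of a death, not of the error, which also needs GvHD therapy at death and a blank stop date.

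**Effect on a group mean.** Assume 20 treated subjects, of whom k match the Day 30/Day 50 case and the others average 60 days.

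- k = 1: true mean (19 × 60 + 21)/20 = 58.05; SAP rule (19 × 60 + 71)/20 = 60.55; +4%.
- k = 2: 56.10 against 61.10; +9%.
- k = 3: 54.15 against 61.65; +14%.
- k = 5: 50.25 against 62.75; +25%.

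**The case against.** **The error needs a particular data state.** The subject must be on GvHD therapy, die before Day 100 and have a blank stop date. Protocol 8.8 and 9.4.4 ask sites to record medications stopped or changed, and Protocol 13.4.2 describes edit checks and queries for completeness. If every site enters a stop date at death, the rule does no harm. This stands as a limit on frequency, which the documents do not let us estimate. It does not remove the defect: no section requires a stop date at death, and the SAP has a branch for blanks because it expects some.

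**A reader might infer that the efficacy claim is affected.** The documents do not support that. Total dose is defined in SAP Section 6, not in the efficacy Section 8, and its table is in the 14.1 series with disposition and demographics. It is not among the visible primary or secondary endpoints (the exploratory rows are redacted). Time to first systemic therapy (SAP 8.8) uses the first start date, and GRFS (SAP 8.7) takes its therapy date from there. For deaths the rule can only raise the GvHD-therapy dose in RGI-2001 subjects, which makes the drug look worse. This SAP has no comparator for the quantity; the CIBMTR comparison is in a separate SAP.

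**A reader might also infer that every early exit is overstated.** That is not supported either. A subject who left alive may have stayed on therapy, so the Day 100 fill counts unobserved dosing, which may or may not have been given.

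**Part of the specification is unseen.** The table shells and the TLF attachment are separate documents and could contain a cut at death or a flag. By-subject medication listings are planned, so affected records could be found. Continuous summaries include the median, which one or two extreme records barely move. All of this is fair, but the derivation in SAP 6.6 is written out in full and should be right as it stands.

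**Conclusion.** The rule is wrong as written for deaths. Any subject who dies before Day 100 on GvHD therapy with a blank stop date is credited with 100 − D days of dosing after death, and Table 14.1.12 overstates total dose to that extent. In the assumed examples the overstatement is 4.4-fold or 3.4-fold for a single subject, and 5 to 55 days across the range examined. The effect of 4% to 25% on a group mean rests on further assumptions about how many subjects are treated and for how long.

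The point is minor. It concerns one descriptive table, its direction is unfavourable to RGI-2001, and it leaves the primary endpoint, time to first systemic therapy and GRFS unchanged. Its frequency is unknown and could be zero. For subjects who left alive, the finding is only that unobserved dosing is counted as received.

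**What to change.** In SAP 6.6, replace the end-date logic as follows:

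- End each record at the earliest of stop date, Day 100 and date of death. The death date is already taken from the Discontinuation eCRF for overall survival (SAP 8.3).
- For subjects who left alive before Day 100 with a blank stop date, count only observed dosing up to last contact, flag the record as incomplete, and note under the table that this may understate the true dose.
- Flag all imputed end dates in the listing.
- List the rule in SAP 4.3 as an exception to the no-imputation statement.

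In the same edit, replace Date_100 in the second branch with the defined name Day100.

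The cost is a few lines of SAP text and a small programming change. No new data are needed, since the SAP already uses a death date and a date last known alive for overall survival.

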7.0 TREATMENT EXPOSURE

Exposure to RGI-2001 will be summarized by the number of doses administered and the duration of exposure. The duration of exposure will be derived as the difference between the first administration date and the last administration date.

Actual dose intensity (µg/kg/day) and the dose intensity (%) relative to the planned dose will be determined and summarized.

A by-subject listings will also be provided.

8.0 EVALUATION OF EFFICACY PARAMETERS

All efficacy analyses will be performed on the Safety Analysis Population. As noted above, outcomes will ultimately be compared to data obtained from the CIBMTR and details of this comparison are contained in a separate SAP that is specific to this goal. Methods for estimation of efficacy parameters are provided below without mention of the methods that will be used for comparing efficacy parameters to the CIBMTR data.

Binary outcomes will be summarized with proportions, continuous outcomes with means and medians, and time-to-event outcomes with Kaplan-Meier estimates or cumulative incidence estimates for endpoints with competing risks.

Definitions of occurrence and timing of outcomes are described below.

8.1 Acute GVHD

For the primary and secondary endpoints as well as certain exploratory endpoints, Keystone criteria will be used for the determination of the severity of aGVHD. For outcomes at a defined time points, the event time will be defined as the time from the “start date” of first RGI-2001 infusion (i.e., transplant date/Day 0) to the first date aGVHD is diagnosed with Keystone criteria Grades II-IV. The first date of aGVHD will be identified using the following eCRFs:

- Initial report: *aGvHD_d* eCRFs with Question 10 = II-IV (i.e., Keystone Grades)
- Maximum report: *aGvHDmax* eCRFs with Question 1 = II-IV (i.e., Keystone Grades)

The first diagnosis date across the eCRFs meeting the above criteria will be used to define the “event time” for this analysis. Censoring: Subjects who are alive without these events will be censored at the date of completion of the last aGVHD assessment, with follow-up truncated at 180 days. Subjects who die without aGVHD will be treated as competing-risk events. The occurrence of aGVHD as a function of time will be calculated using cumulative-incidence estimates.

As an exploratory outcome, MAGIC criteria will be used for the determination of the severity of aGVHD. Event time will be defined as the time from the “start date” of first RGI-2001 infusion to the first date aGVHD is diagnosed with MAGIC criteria Grades II-IV. The first date will be identified using the following eCRFs:

- Initial report: *aGvHD_d* eCRFs with Question 8 = II-IV (i.e., MAGIC Grades)
- Maximum report: *aGvHDmax* eCRFs with any of the following three categories:
 - Grade II: Stage 3 skin and/or stage 1 liver and/or stage 1 upper GI and/or stage 1 lower GI (questions 3,4,5, and 6 on the eCRF)
 - Grade III: Stage 2-3 liver and/or stage 2-3 lower GI, with stage 0-3 skin and/or stage 0-1 upper GI
 - Grade IV: Stage 4 skin, liver, or lower GI involvement, with stage 0-1 upper GI

The first diagnosis date across the eCRFs meeting the above criteria will be used to define the “event time” for this analysis. Censoring and competing-risk considerations will be the same as with the Keystone criteria (above). The occurrence of aGVHD as a function of time will be calculated using cumulative-incidence estimates.

Similar to above, the analysis will be repeated for Keystone and Magic separately using only Grades III and IV.

8.2 Chronic GvHD

Chronic GvHD (cGvHD) will be summarized visually as a function of time up to one year as a cumulative incidence estimates as well as by-visit frequency analysis.

Severity ratings according to 2014 NIH Criteria will be used. Event time will be defined as the time from the “start date” of first RGI-2001 infusion (i.e., transplant date) to the first date cGvHD is diagnosed with moderate or severe cGvHD (if multiple cGvHD_d eCRFs exist with moderate/severe ratings, the first diagnosis date across the eCRFs will be used for this event). Censoring: Subjects who are alive without these events will be censored at the date of completion of the last cGvHD assessment, with follow-up truncated at one year (365 days). Subjects who die or relapse without cGVHD will be treated as competing-risk events at the time of death. The occurrence of cGVHD as a function of time will be calculated using cumulative-incidence estimates.

Similar to above, the analysis will be repeated for using all severities (not just moderate and severe).

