8.4 Disease-Free Survival (DFS)

DFS rates (synonymous with Relapse-Free Survival [RFS]) will be calculated using Kaplan-Meier methodology. For each subject, DFS will be calculated as time from the “start date” of first RGI-2001 infusion to relapse, disease progression, or death from any cause, whichever occurs first. Censoring: Subjects who do not experience any DFS events will be censored on the last evaluation of relapse/progression (using the *Disease Status Follow-up* eCRF), with follow-up not extending beyond one year. There are no competing risk events. Kaplan-Meier estimates of this endpoint as a function of time will be provide for visual purposes.

Date of first relapse will be obtained using the *Disease Status Follow-up* eCRF where Question 7 “Disease Status” = “1st relapse” or “Relapse from complete remission”. This eCRF contains three dates: Question 1 Date of Bone Marrow Aspirate, Question 2 Date of Bone Marrow Biopsy, and Visit Date. If multiple dates are provided, the first will be used to define the Date of First Relapse.

Date of first progression will be obtained using the *Disease Status Follow-up* eCRF where Question 7 “Disease Status” = “Progression from hematologic improvement”. Similar to relapse, the first of the three dates will be used to define the Date of First Progression.

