8.5 Non-Relapse Mortality (NRM)

Non-relapse mortality (NRM) rates will be calculated using a cumulative incidence estimate for visual purposes. NRM will be defined as the occurrence of death without prior relapse, with relapse a competing risk for NRM. For each subject, time to death will be calculated as described in the above OS section and time to relapse will be calculated as described in the DFS section.

Event and censoring assignments will proceed as follows:

- Subjects with no relapse and no death will be censored at the last time known to be alive.
- Subjects with no relapse who die will be counted as events.
- Subjects with relapse will be considered a competing risk at the time of first relapse.
- Follow-up will not extend beyond one year.

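### SAP 8.2 names relapse as a competing event for chronic GvHD but dates it at death, so as written relapse never competes at its own date

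*SAP*

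**What the plan says.** SAP 8.2 estimates cGvHD by cumulative incidence, with follow-up cut at 365 days, first for moderate or severe disease and then for all severities. Its rule for competing events is: "Subjects who die or relapse without cGVHD will be treated as competing-risk events at the time of death". The sentence before it gives the censoring rule: "Subjects who are alive without these events will be censored at the date of completion of the last cGvHD assessment". That rule makes no exception for relapse.

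Two neighbouring sections bear on the date. SAP 8.4 derives a date of first relapse from the *Disease Status Follow-up* eCRF. SAP 8.5 uses that date for non-relapse mortality: "Subjects with relapse will be considered a competing risk at the time of first relapse".

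Protocol 12.3.1 calls for cumulative incidence where there are competing risks, but does not say how a competing relapse is dated. Total and moderate-severe cGvHD at 6 months and 1 year are secondary endpoints (Protocol 5; SAP 1.1).

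**The concern.** A competing event takes a subject out of the risk set on the day it happens. SAP 8.2 names two such events but gives a date for only one. A programmer who follows the sentence literally keeps relapsed subjects at risk until death and censors those who stay alive. A programmer who reads it as a slip dates them at relapse. The two can report different cGvHD rates from the same data.

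More than a date is at stake. If relapse competes at its own date, cGvHD that first appears after relapse is not an event. If it does not compete, that cGvHD is an event. These are different quantities, and the SAP should say which one it reports. Under the literal reading the estimate also depends on how long relapsed subjects stay under cGvHD assessment, which has nothing to do with the treatment.

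**Working it through.** The plan states no figure that depends on this rule, so there is nothing to reproduce. The defect follows from the wording; the size needs assumed data.

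**Step 1. Apply SAP 8.2 to each kind of relapsed subject.**

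| Course | SAP 8.2 as written | Relapse dated at first relapse (as in 8.5) |
|---|---|---|
| Relapse, then death, no cGvHD | Competing event at death; the word die alone gives this | Competing event at relapse |
| Relapse, alive, no cGvHD | No death date; censored at last cGvHD assessment | Competing event at relapse |
| Relapse, then cGvHD | Still at risk, so a cGvHD event | Competing event at relapse; later cGvHD not counted |

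In no row does relapse act on its own date. The middle column would be the same if relapse were not mentioned.

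**Step 2. Size in a 50-subject example.** N = 50 is from SAP 2.3; everything else is assumed.
- Non-relapse deaths: days 40, 90, 150, 210, 300.
- cGvHD: 12 cases evenly spaced from day 115 to day 345.
- Relapse then death: days 80/150, 120/220, 160/260, 200/320.
- Living relapsers: 2, 4 or 6, evenly spaced from day 70 to day 240.
- All others event-free to day 365.

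The estimator is Aalen-Johansen. With nobody censored before day 365, each subject carries weight 1/50, so relapse dated at relapse gives 12/50 = 24.0%. When a subject is censored early, that weight is shared equally among those still at risk.

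As written, with 2 living relapsers (days 70 and 240) last assessed at relapse:
- After day 70, 48 remain (50, less one death, less one censored). Weight = (1/50) × (1 + 1/48) = 0.020417.
- By day 240, 6 cGvHD cases have occurred. Still at risk after day 240 are 6 later cGvHD cases, 1 later non-relapse death, 2 relapsers who die later and 27 event-free subjects, 36 in all. Weight = 0.020417 × (1 + 1/36) = 0.020984.
- One-year incidence = 6 × 0.020417 + 6 × 0.020984 = 0.1225 + 0.1259 = 24.8%.

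One-year results for 2 / 4 / 6 living relapsers:

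| Rule and last cGvHD assessment | 12 cGvHD cases |
|---|---|
| Relapse dated at relapse | 24.0 / 24.0 / 24.0% |
| As written, last assessed at relapse | 24.8 / 25.8 / 26.9% |
| As written, last assessed 90 days after relapse | 24.5 / 25.2 / 25.8% |
| As written, assessed to day 365 | 24.0 / 24.0 / 24.0% |

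With last assessment at relapse, the shift is +0.5 to +1.9 points for 8 cGvHD cases and +1.3 to +4.4 for 18. At day 180 the largest shift is 0.6 (10.0 against 10.6%, with 18 cases).

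**Step 3. cGvHD after relapse.** With assessment to day 365, each onset after relapse adds 1/50 = 2.0 points: 24.0% becomes 26.0, 28.0 or 30.0% with one, two or three.

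**Step 4. Wider assumptions.** A simulation of 100,000 subjects per setting assumed one-year latent risks of 30% for cGvHD, 10% for non-relapse death and 20, 30 or 40% for relapse, with median survival of 180 days after relapse. The two rules differed by 0 to about 6 points. Zero occurred with assessment to day 365 and no onset after relapse. The top of the range needed 40% relapse, an undiminished cGvHD hazard after relapse, and living relapsers without cGvHD censored at relapse.

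**Step 5. Sampling error.** The binomial standard error at 27% is √(0.27 × 0.73 / 50) = 6.3 points.

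**The case against.** The strongest reply is that the sentence is an obvious slip. It expressly makes relapsed subjects competing events, SAP 8.4 and 8.5 supply the date and show its use, and a sensible programmer would fill the gap. That may be what was meant. The SAP does not say so, however, and its own censoring sentence gives living relapsers another destination.

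The second reply concerns size, and it stands. The protocol schedules GvHD assessment at visits through Day 365 and, in footnote p of the Schedule of Assessments, to the end of study. Section 6 sets a minimum of Day 100, Day 180 and one year. With that follow-up and no onset after relapse, the two rules agree in the example. A difference needs assessment to stop early after relapse, or cGvHD to begin after relapse. SAP 8.2 also plans a by-visit frequency analysis, and SAP 11.3 plans listings of time-to-event data, so the dating used could be checked afterwards.

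A reader might also infer more than the documents support:
- **Non-relapse mortality.** SAP 8.5 names relapse but not progression, while DFS counts "relapse, disease progression, or death from any cause, whichever occurs first". This is not an error in 8.5. It sends the reader to the DFS section for time to relapse, and 8.4 codes and dates relapse and progression separately. Whether progression should also compete is a choice of estimand.
- **Acute GvHD.** SAP 8.1 names only death: "Subjects who die without aGVHD will be treated as competing-risk events". Different endpoints may have different competing events, so the contrast alone shows no fault.
- **The treatment comparison.** SAP 8.0 places the CIBMTR methods in a separate SAP that is not available here. No effect on that comparison can be shown or excluded.

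**Conclusion.** The point holds for cGvHD alone. SAP 8.2 states a rule that defeats its own wording: relapse is listed as competing but never takes effect on its own date, and whether cGvHD after relapse counts is left to a date clause that may be a slip. This follows from the text and needs no assumption.

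The size is modest and rests wholly on assumed data. In the main 50-subject example the shift at one year is 0 to 2.9 points without onsets after relapse, plus 2.0 points for each such onset. Up to two onsets stay below the standard error of about 6 points. Three onsets, or the extreme of the simulation, come to about one standard error. The primary acute GvHD endpoint is not touched, and the cGvHD estimates under this SAP are descriptive. The matter should be corrected before analysis because it decides what a secondary endpoint measures; it does not threaten the trial's main conclusion.

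**What to change.** In SAP 8.2, date the competing event at the earlier of first relapse (the 8.4 date) and death, in subjects without prior cGvHD. If the sponsor instead wants cGvHD after relapse to count, delete the reference to relapse and say so. Either version applies to both severity analyses. Progression need not be added, since 8.2 does not name it.

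Before choosing, check how the separate CIBMTR comparison SAP defines this event for controls, and use one definition in both groups.

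The cost is one clause of SAP wording. The relapse date is already derived for DFS, so no new data are needed.
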